**a) Forward Procedure:**

We define the forward variables at  $t = 1, \dots, T$  as:

$$\alpha_i(t) = \sum_{\mathbf{h}_{1:t-1}} P(H_1 = h_1, \dots, H_{t-1} = h_{t-1}, H_t = i) \prod_{j=1}^{t-1} q(h_j^{obs}, h_j) q(h_t^{obs}, i), \quad i = 1, \dots, 8.$$

When the product  $\prod_{j=1}^{t-1} q(h_j^{obs}, h_j)$  has the upper bound less than the lower bound we define the product as 1, that is  $\alpha_i(1) = P(H_1 = i) q(h_1^{obs}, i) = \pi_i q(h_1^{obs}, i)$ .

For  $t \geq 2$  we may write the forward variables as:

$$\alpha_i(t) = \sum_{\mathbf{h}_{1:t-1}} \pi_{h_1} q(h_1^{obs}, h_1) \left( \prod_{j=1}^{t-2} P_{b_j}(h_{j+1} | h_j) q(h_{j+1}^{obs}, h_{j+1}) \right) P_{b_{t-1}}(i | h_{t-1}) q(h_t^{obs}, i).$$

$\alpha_i(t)$  may be calculated using the recursion formula:

$$\begin{aligned} \alpha_i(1) &= \pi_i q(h_1^{obs}, i) \\ \alpha_i(t) &= q(h_t^{obs}, i) \sum_{j=1}^8 \alpha_j(t-1) P_{b_{t-1}}(i | j), \quad t = 2, \dots, T. \end{aligned}$$

To make the algorithm more numerically stable and tackle the underflow problem, we follow the commonly used normalized forward algorithm. The likelihood until time  $t$  is:

$$L(\mathbf{h}_{1:t}^{obs}) = \sum_{i=1}^8 \alpha_i(t).$$

Then, we can introduce normalized forward variables as:

$$\alpha_i^*(t) = \frac{\alpha_i(t)}{L(\mathbf{h}_{1:t}^{obs})}.$$

From the recursion formula above, we have:

$$\alpha_i^*(t) = \frac{L(h_{1:t}^{obs})}{L(h_{1:t-1}^{obs})} q(h_t^{obs}, i) \sum_{j=1}^8 \alpha_j^*(t-1) P_{b_{t-1}}(i|j), \quad t = 2, \dots, T.$$

Define:

$$c_t = \frac{L(h_{1:t}^{obs})}{L(h_{1:t-1}^{obs})}, \quad t = 1, \dots, T,$$

where:  $c_1 = L(h_1^{obs}) = \sum_{i=1}^8 \alpha_i(t)$ . Then,

$$c_t = \sum_{i=1}^8 q(h_t^{obs}, i) \sum_{j=1}^8 \alpha_j^*(t-1) P_{b_{t-1}}(i|j), \quad t = 2, \dots, T,$$

and:

$$L(h_{1:T}^{obs}) = \prod_{t=1}^T c_t.$$

#### b) Backwards Procedure:

We define the backwards variables at  $t = 1, \dots, T$  as:

$$\beta_i(t) = \sum_{h_{t+1:T}} P(H_{t+1} = h_{t+1}, \dots, H_T = h_T | H_t = i) \prod_{j=t+1}^T q(h_j^{obs}, h_j).$$

These may be calculated using the recursion formula:

$$\beta_i(T) = 1$$

$$\beta_i(t) = \sum_{j=1}^8 \beta_j(t+1) P_{b_t}(h_{t+1} = j|i) q(h_{t+1}^{obs}, j).$$

Similarly, we can define normalized backward variables as:

$$\beta_i^*(t) = \frac{L(h_{1:t}^{obs})}{L(h_{1:T}^{obs})} \beta_i(t), \quad t = 1, \dots, T,$$

with  $\beta_i^*(T) = 1$ . The normalized recursion formula is:

$$\beta_i^*(t) = \frac{1}{c_{t+1}} \sum_{j=1}^8 \beta_j^*(t+1) P_{b_t}(h_{t+1} = j|i) q(h_{t+1}^{obs}, j), \quad t = T-1, \dots, 1.$$

c) **Baum Welch (i.e., EM) Procedure:**

Define the quantities:

$$\begin{aligned}\gamma_i(t) &= P(H_t = i | H_{1:T}^{obs}) \\ &= \frac{\beta_i(t)\alpha_i(t)}{\sum_{j=1}^8 \beta_j(t)\alpha_j(t)} = \frac{\beta_i(t)\alpha_i(t)}{L(\theta | H_{1:T}^{obs})} = \beta_i^*(t)\alpha_i^*(t),\end{aligned}$$

And:

$$\begin{aligned}\xi_{ij}(t) &= P(H_t = i, H_{t+1} = j | H_{1:T}^{obs}) \\ &= \frac{\alpha_i(t)P_{b_t}(j|i)\beta_j(t+1)q(h_{t+1}^{obs}, j)}{\sum_{s=1}^8 \sum_{u=1}^8 \alpha_s(t)P_{b_t}(u|s)\beta_u(t+1)q(h_{t+1}^{obs}, u)} \\ &= \frac{\alpha_i(t)P_{b_t}(j|i)\beta_j(t+1)q(h_{t+1}^{obs}, j)}{L(\theta | H_{1:T}^{obs})} \\ &= \frac{\alpha_i^*(t)P_{b_t}(j|i)\beta_j^*(t+1)q(h_{t+1}^{obs}, j)}{c_{t+1}}.\end{aligned}$$

Then, we can update  $\theta$  as following:

$$\pi_i^* = \gamma_i(1),$$

$$P_b^*(j|i) = \frac{\sum_{t \in \{t: b_t = b\}} \xi_{ij}(t)}{\sum_{t \in \{t: b_t = b\}} \gamma_i(t)}.$$

The convergency criteria is set by change of likelihood value between two consecutive steps is numerically indistinguishable.

4) **Simulating missing states (i.e., simulating from  $P_\theta(H^{mis} | H_{1:T}^{obs})$ ):**

First the backward and forward algorithms are calculated for each patient.

Next, for each patient we follow the following procedure:

1. Simulate  $h_1$  from the discrete distribution defined by the vector of probabilities  $(\gamma_1(1), \dots, \gamma_8(1))$ .
2. For  $t > 1$ , simulate  $h_t$  from the discrete distribution defined by the vector of probabilities  $(\xi_{h_{t-1}1}(t-1), \dots, \xi_{h_{t-1}8}(t-1))/\zeta$  where  $\zeta$  is a normalizing constant,  $\sum_{i=1}^8 \xi_{h_{t-1}i}(t-1)$ .

## Appendix 3. Exploratory Analyses

### 1) Additional analyses for the main study (through Day 28)

The primary analysis (progression to ventilation or death by Day 28) and time to recovery will be repeated for the following subgroups, if sample sizes allow:

- No baseline steroids, no baseline remdesivir
- No baseline steroids, yes baseline remdesivir
- Yes baseline steroids, no baseline remdesivir
- Yes baseline steroids, yes baseline remdesivir

#### 1.1) Additional analyses for the main study (Day 60)

The following table gives planned analyses for the main study using Day 60 data.

Variable	Population	Analysis Method	Time Point	Groups/Subgroups
Observed OS values at Day 60	ITT population with a baseline NIAID OS and a value at the Day 60 Visit	Descriptive statistics as described in Table KHAA.6.1 for categorical/discrete data.	At the Day 60 visit.	Overall and by baseline 
 
• OS 4, 5, 6 and 5, 6 combined.
 
• Corticosteroid status (see Section 6.1.4)
 
• Age group (<65, ≥65)
 

All-cause mortality:	Patients in the ITT population, excluding randomized patients who discontinued on the day of randomization and have no baseline or postbaseline OS data.	Time to death from all causes, all time on study. Event dates are date of death for patients who died. Censor dates are last known information that indicates patient was alive. Patients who die after the visit window for Day 60, will be censored at the last date of their Day 60 visit window. KM curves and standard summary statistics (see Section 6.2.3 ) will be generated.	From baseline to end of study participation.	

Additionally, the following analyses will be performed after the Day 60 database lock for relevant subsets of the ITT population.

- Demographics
- Disposition
- Concomitant medications
- Safety analyses will include all adverse events occurring post primary outcome datalock up to an including Day 60. The following are the planned safety analyses:
  - Follow-up-emergent adverse events (FEAEs). FEAE is defined as an event that either first occurred or worsened in severity after Day 28 and on or prior to end of the study.
  - Serious adverse events
  - Adverse events leading to death
  - Overview of infections (includes herpes zoster, herpes simplex, opportunistic infections, and tuberculosis)

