## 8.1. Efficacy Assessments

## 8.1.1. COVID-19 Clinical Status Assessment

The COVID-19 Clinical Status Assessment will be used to collect components needed to derive scores for the ordinal scales used in this study. This assessment will also collect the use of proning and reason for discontinuation of invasive mechanical ventilation.

The assessment will be completed on each day of the study by entering the assessment for the previous day (that is, midnight to midnight; 00:00 - 23:59 [24 hour clock]).

On Day 1, the patient's status at randomization will be reported.

On Day 2 the status will be reported for the period from randomization to midnight on Day 1.

The patient's clinical status will be captured daily through Day 29.

The hospitalization portion of the patient's clinical status will be completed daily, regardless of patient's discharge status or patient contact.

The patient's clinical status reflecting data for Day 28 (midnight to midnight) will be recorded in the Day 29 eCRF.

A clinical status assessment will be conducted via telephone visit for Day 60.

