**Table KHAA.6.1. General Methods for Statistical Analysis**

Data Type	Purpose	Analysis
Categorical/discrete data	Summary and descriptive analysis	Number of patients with available data (n), either observed or imputed, at the relevant time point, and will be presented as frequency counts and percentages. Percentages will be calculated using the total number of patients in the analysis population included as the denominator. Percentages will generally be presented to 1 decimal place but will not be presented for zero counts.
	Treatment comparison	Logistic regression analysis
Continuous data	Summary and descriptive analysis	Number of observations, mean, standard deviation (SD), standard error of the mean (SEM), median, 1st quartile, 3rd quartile, minimum, and maximum. The minimum and maximum will be reported to the same number of decimal places as the raw data recorded in the database. The mean, first quartile, median, and third quartile will be reported to 1 more decimal place than the raw data recorded in the database. The SD and SEM may be reported to 2 more decimal places than the raw data recorded in the database. Any exceptions will be noted in the programming specifications. P-values for primary and key secondary analyses will be reported to as many decimal places as needed ( $\geq 5$ ).
	Treatment comparison	Analysis of variance (ANOVA), mixed model repeated measures (MMRM), Wilcoxon rank-sum test
Ordinal data	Treatment comparison	Proportional Odds model, Wilcoxon rank-sum test
Time to event data	Treatment comparison	Log-rank test, Kaplan-Meier curves, Cox proportional hazards. As needed: Fine-Gray model, Max-combo test

Note: the detail of the analysis method defined in Section 6.2.

Change from baseline will be calculated as the visit value of interest minus the baseline value. If the baseline value is missing for a particular variable, then it will not be imputed and the change from baseline and percent change (or percent improvement) from baseline will not be calculated.

For all models, patients will be excluded who do not have the necessary covariates to run the model.

For the primary and key secondary analyses that rely on OS values, the patient's worst ordinal score for the day will be used.

The Per Protocol Set (PPS) will be used if needed for post hoc analyses.

Throughout this document, "Day x" refers to Study Day x.

Additional supportive analyses will be performed as needed.

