### 6.4.3. Multiple Imputation

A multiple imputation method will be used to impute the missing NIAID-OS scores (Rubin, 1996). The multiply-imputed datasets will be used for the primary analyses of several endpoints involving the NIAID-OS scores. A total of 100 multiply-imputed datasets will be generated. For random number generation, the seed will be set 3012021. The multiple imputation will be performed in a stratified manner with the imputation performed separately for each of the following levels: (1) baricitinib patients with baseline NIAID-OS of 5 or 6 and baseline steroid use, (2) baricitinib patients with baseline NIAID-OS of 5 or 6 and no baseline steroid use, (3) other baricitinib patients, (4) comparator patients with baseline NIAID-OS of 5 or 6 and baseline steroid use, (5) comparator patients with baseline NIAID-OS of 5 or 6 and no baseline steroid use, and (6) other comparator patients. In all these strata, baseline steroid use is defined as in Section 6.1.4. These strata are slightly reduced from what might be expected in order to keep a sufficient number of patients in each stratum. Imputation will be performed using a Markov model where each transition to a future state is dependent on only the previous state. This approach is described in detail in [Appendix 2](#).

The intended estimand for the multiple imputation approach is based on the treatment policy strategy for handling intercurrent events (ICH E9R [ICH 2017]). In this strategy the value of the NIAID-OS score is the value of interest regardless of any intercurrent events that occurred. The NIAID-OS includes a state for death, and thus it is meaningful even for patients who have died.

If the between-imputation variance calculated while combining some analysis results of the multiply-imputed datasets is zero then that specific analysis will not be performed using multiple imputation. Instead, the observed data will be used to perform the same analysis.

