	5. Hospitalized, requiring supplemental oxygen	Duration of hospitalization	Total number of days patients have a NIAID-OS of 4, 5, 6, or 7. If the patient died on or prior to Day 28, their duration of hospitalization is considered to be 28 days. On Day 1 the patient's worst ordinal scale between baseline and the rest of Day 1 will be used to define their hospitalization status.	Missing if patient's NIAID-OS is missing for any day
	6. Hospitalized, on noninvasive ventilation or high-flow oxygen devices			
7. Hospitalized, on invasive mechanical ventilation or ECMO				
8. Death				

Measure	Description	Variable	Derivation / Comment	Definition of Missing
		All-cause mortality	Time to death by Day 28. Patients included: ITT population Start date: Baseline date Event date: date of death if death is within 28 days of their baseline date. (That is, if baseline is Day 1, any deaths up to and including Day 28 are included). Censor date: Date of last non-missing OS or visit that is on or prior to Day 28. If there is other information that makes it clear that they were alive at Day 28, they will be censored at Day 28.	Missing if the patient's maximum NIAID-OS is not 8 and patient's NIAID-OS is missing for all days after a particular day
Oxygen Saturation	Measure of the oxygen level of the blood measured by pulse oximetry	Oxygen saturation from <94% at baseline to ≥94% (at days 4, 7, 10 and 14)	Patients included: randomized patients whose oxygen saturation (based on NEWS) is < 94% at baseline. A patient is a responder at Day x if their oxygen saturation is ≥ 94% and their OS is not higher than their baseline OS. Otherwise, they are a non-responder. Patients who are missing data at Day x due to having died are considered to be non-responders.	Missing if either baseline or observed oxygen saturation measurement is missing

Abbreviations: ECMO = extracorporeal membrane oxygenation; NIAID-OS = National Institute of Allergy and Infectious Diseases ordinal scale.

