### 1) Unique challenges for multiple imputation of the NIAID-OS:

While many methods of multiple imputation (and single imputation) are readily available in standard software, the NIAID-OS in KHAA presents several unique problems. First, it includes an absorbing state of death (NIAID-OS = 8). Also, complete recovery (NIAID-OS = 1) is ordinarily an absorbing state with some exceptions where patients become sick again. Second, change between days is generally slow. Patients often stay in the same state for several days. Thus, the correlation between days is very strong which may cause issues of (near) multicollinearity when fitting regression models for use in imputation. Also, some methods may not converge when many highly correlated days are being imputed for a patient. Third, standard assumptions such as multivariate normality and approximate linearity are highly suspect for the NIAID-OS. Finally, for study KHAA additional information is available for some patients. For example, for many patients the exact NIAID-OS score is missing for some days, but it may be inferred from other available data that the patient is not dead (i.e., NIAID OS  $\neq$  8). It would be beneficial to use an imputation technique which can make use of this information.

For these reasons, a novel Markov model multiple imputation (MMMI) method is adopted to impute the NIAID-OS scores. A simulation study was performed to show the operating characteristics of the suggested method. The manuscript for this method is currently under preparation and the results of the simulation study are available upon request.

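### The exploratory Day 60 ordinal-scale table, read as written, leaves out patients who died before Day 60, so its percentages by arm are conditioned on survival

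*SAP*

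**What the plan says.** SAP Appendix 3, section 1.1, plans two outcome rows using Day 60 data.

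- **Ordinal scale.** The variable is "Observed OS values at Day 60". The population is the "ITT population with a baseline NIAID OS and a value at the Day 60 Visit", the time point is the Day 60 visit, and the method is descriptive statistics for categorical data, overall and by baseline OS, corticosteroid status and age group.
- **All-cause mortality.** Time to death over all time on study, in nearly the whole ITT population, with Kaplan-Meier curves. No Day 60 value is required. Deaths after the Day 60 visit window are censored at the end of that window.

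Section 2 of the same appendix repeats the ordinal-scale population for the Addendum 5 patients, who are at OS 7 at baseline, and also has a mortality row.

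For categorical data, Table KHAA.6.1 sets the denominator: "Percentages will be calculated using the total number of patients in the analysis population included as the denominator". On data collection, Protocol 8.1.1 has clinical status recorded daily through Day 29, and then: "A clinical status assessment will be conducted via telephone visit for Day 60". Long-term outcomes are listed as exploratory in SAP 4.3.

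**The concern.** Death is a state of the NIAID-OS, so a patient who died on Day 20 has a known and very bad status at Day 60. That patient cannot take a telephone call at Day 60. If only patients with a visit value are tabulated, the death category is nearly empty and every other percentage is inflated by the share who died.

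The inflation is larger in the arm with more deaths. If the drug keeps some very ill patients alive, they appear in its Day 60 table at poor scores, while comparable placebo patients are absent. A table meant to show longer-term clinical status could then flatter the arm with worse survival. Protocol 4.2 says that the Day 60 evaluation was added on regulatory feedback to look at safety and effectiveness. Besides mortality, this is the only efficacy row in the main-study Day 60 table.

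**Working it through.** The plan states no figure for this table, so there is none to reproduce. The check has two parts.

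**1. Does the written rule leave out earlier deaths?**

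- *Data collection.* Daily status ends at Day 29 (Protocol 8.1.1), and the next assessment is the Day 60 telephone visit. Neither document describes a Day 60 score being recorded for a patient who died before it.
- *The word observed.* Table KHAA.6.7 lists the severity categories once as observed and once with LOCF, so the SAP treats these as different things. The Day 60 row specifies observed values and no carry-forward.
- *The statements about death on the scale.* SAP 6.4.3 says: "The NIAID-OS includes a state for death, and thus it is meaningful even for patients who have died". Appendix 2 calls death an absorbing state. Both belong to the Markov imputation, which has 6 + 7 + 7 + 7 = 27 daily transitions. That takes Day 1 to Day 28 and no further.
- *Death rules elsewhere.* For oxygen saturation, Table KHAA.6.4 says: "Patients who are missing data at Day x due to having died are considered to be non-responders". There are also written rules for duration of hospitalisation (Table KHAA.6.4), time to recovery (SAP 6.4.1), and ICU stay and extubation (Table KHAA.6.6). The Day 60 OS row has none.

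Together these make exclusion of earlier deaths the natural reading, though the text does not state it in so many words.

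**2. What would exclusion do to the percentages?**

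Let *s* be the share of all randomised patients in a good category and *m* the share dead by Day 60. With complete follow-up of survivors, the table shows *s*/(1 − *m*) instead of *s*. All values of *s* and *m* below are assumptions; only the planned total of 1400 (700 per arm) is from the documents.

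*Equal mortality, s = 70% at OS 1-2 in both arms:*

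| Mortality | Patients removed of 1400 | Table shows |
|---|---|---|
| 5% | 70 | 0.70/0.95 = 73.7% |
| 10% | 140 | 0.70/0.90 = 77.8% |
| 15% | 210 | 0.70/0.85 = 82.4% |

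*Unequal mortality:*

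| Mortality, placebo / baricitinib | Good outcome in all randomised, placebo / baricitinib | True difference (points) | Table shows, placebo / baricitinib | Shown difference (points) |
|---|---|---|---|---|
| 10% / 5% | 70% / 70% | 0 | 77.8% / 73.7% | −4.1 |
| 15% / 10% | 70% / 70% | 0 | 82.4% / 77.8% | −4.6 |
| 20% / 10% | 70% / 70% | 0 | 87.5% / 77.8% | −9.7 |
| 15% / 10% | 60% / 64% | 4.0 | 70.6% / 71.1% | 0.5 |
| 20% / 15% | 55% / 59% | 4.0 | 68.8% / 69.4% | 0.7 |
| 15% / 10% | 60% / 68% | 8.0 | 70.6% / 75.6% | 5.0 |

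The sign of a true gain reverses when the ratio of the good-outcome shares (baricitinib to placebo) is above 1 but below the ratio of the survival shares. With 15% and 10% mortality the latter is 0.90/0.85 = 1.059. From 60% on placebo, any baricitinib share between 60% and 0.60 × 1.059 = 63.5% would appear as a loss.

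**The case against.** Three arguments deserve weight.

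*The documents do not expressly exclude deaths.* OS 8 is a value of the scale. Protocol 8.1.2 has scores derived from data already in the eCRF, and SAP 6.4 allows NIAID-OS outcomes to be derived from other clinical data before imputation. A programmer could tabulate a known death as OS 8 within that framework. This stands as a possible reading. But the SAP 6.4 wording is permissive, and nothing in the Day 60 row invokes it. Two programmers could therefore produce different tables.

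*The deaths are not hidden.* A reader might infer that the long-term outcome is reported in survivors only. The documents do not support that. The adjacent row in each table analyses all-cause mortality to the end of the Day 60 window without requiring a Day 60 value, and adverse events leading to death are also reported for the main study. A mortality difference would be seen there. That row does not correct the OS distribution, however; readers would have to combine two rows with different populations themselves.

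*The analysis carries no inference.* The row is exploratory and descriptive, with no test and no place in the graphical testing scheme. This stands in full. Table KHAA.6.1 also reports the number with available data, and disposition is rerun after the Day 60 lock, so much of the loss would be visible, though not as a count of unknown Day 60 status.

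**Conclusion.** The point holds for the ordinal-scale row in both Appendix 3 tables. As written, the population rule conditions the Day 60 distribution on survival, and the result can understate or reverse a difference between arms. It affects one descriptive, exploratory table per cohort and no primary, key secondary or other secondary result.

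The size is unknown. The documents give neither Day 60 mortality nor a Day 60 OS distribution, so every figure above rests on assumed rates and on complete follow-up of survivors. A reader might infer from the 60% / 64% case that nearly all of a benefit would vanish: (4.0 − 0.5)/4.0 is roughly 87%. That depends on pairing a 5-point mortality gain with a smaller gain in good outcomes. With 60% / 68% and the same mortality, 5.0 of 8.0 points remain. Nor do the documents give a figure to support a claim that the distortion is larger in Addendum 5, even though those patients start on invasive ventilation. What does not depend on the assumed rates is that a survivor-only percentage differs from the all-patient percentage whenever there are deaths, and by more in the arm with the higher mortality if the all-patient percentages are equal.

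**What to change.** In both Appendix 3 tables, define the ordinal-scale population as ITT patients with a baseline NIAID-OS and either a Day 60 value or death on or before the end of the Day 60 visit window. Tabulate those deaths as OS 8. The cut-off then matches the mortality row.

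Add a line giving the number of patients with unknown Day 60 status, by arm. This is needed alongside the first change. If a share *u* of patients is alive or of unknown status without a Day 60 value and is left out, the death percentage reads *m*/(1 − *u*) and is inflated unless *u* is shown.

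The cost is one sentence in each table and one extra line of output. Death dates are already needed for the mortality row, so no new data are required.
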